1.6.3. JTX-2011 in Combination with Ipilimumab

Based on clinical data with ipilimumab, there is a risk of severe and potentially fatal acute immune-mediated adverse events due to T-cell activation and proliferation, which may involve any organ system. The most common reactions are: enterocolitis, hepatitis, dermatitis (including toxic epidermal necrolysis), neuropathy and endocrinopathy (Yervoy® Full Prescribing Information {Bristol-Myers Squibb Company 2017b}). The majority of these immune-mediated reactions manifest during treatment. However, they may occur weeks to months after discontinuation of ipilimumab. Adverse events associated with administration of ipilimumab may be increased in frequency or severity when combined with JTX-2011.

In vitro studies of cytokine induction with the combination of ipilimumab and JTX-2011 in human PBMCs and whole blood were performed, and no indication of cytokine storm was observed {JTX-2011 022}.

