3.6. Study Drug

Study drug is hereby defined as JTX-2011 monotherapy and JTX-2011 in combination with nivolumab, ipilimumab, or pembrolizumab.

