5.3. Part E (JTX-2011 in Combination with Ipilimumab Dose Escalation)

Part E comprises escalating doses of JTX-2011 in combination with ipilimumab in consecutive cohorts (JTX-2011 will be administered IV q6w and will be administered until a subject meets criteria for discontinuation; ipilimumab will be administered IV q3w for up to 4 doses).

Three (3) dose escalation cohorts are planned at doses of 0.03 mg/kg, 0.1 mg/kg, and 0.3 mg/kg (approximately 3 dose levels with a minimum of 3 or up to 6 subjects per dose level, exclusive of replacement subjects and evaluation of escalation dose levels [approximately 18 subjects]). A dose de-escalation cohort of 0.01 mg/kg of JTX-2011 may be explored.

Table 3: Part E Dose Escalation Schema

Cohort	JTX-2011 Dose
E63	0.3 mg/kg
E62	0.1 mg/kg
E61*	0.03 mg/kg
E60	0.01 mg/kg

* Starting dose level

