6.3. Definition of Dose Limiting Toxicity (DLT)

A DLT is defined as any of the following study drug-related toxicities (defined as at least possibly related to study drug) **occurring in the first cycle** of study treatment:

Hematological:

- \geq Grade 4 neutropenia lasting > 7 days;
- Febrile neutropenia;
- Any Grade 3 thrombocytopenia with bleeding or a requirement for platelet transfusions;
- \geq Grade 4 thrombocytopenia (platelets $< 25,000/\mu\text{L}$).

Non-hematological:

- AST or ALT $> 3 \times$ ULN and concurrent total bilirubin $> 2 \times$ ULN without initial findings of cholestasis (e.g. findings consistent with Hy's law or FDA definition of potential drug-induced liver injury [pDILI]);
- \geq Grade 4 AST or ALT of any duration;
- Any \geq Grade 3 non-hematologic toxicity with the following exceptions:
 - Grade 3 immune-related AE (irAE) that resolves to \leq Grade 1 or to baseline with immunosuppressive therapy within 3 weeks;
 - Grade 3 fatigue that persists < 7 days;
 - Grade 3 rash that resolves to \leq Grade 1 within 3 weeks;
 - Grade 3 or 4 elevation in serum amylase and/or lipase that are not associated with clinical or radiographic evidence of pancreatitis;

- \geq Grade 3 electrolyte abnormality that lasts $<$ 72 hours, is not clinically complicated, and resolves spontaneously or responds to conventional medical intervention;
- Grade 3 nausea or vomiting that lasts $<$ 48 hours, and resolves to \leq Grade 1 either spontaneously or with conventional medical intervention;
- Grade 3 infusion reaction that resolves within 6 hours to \leq Grade 1;
- Alopecia;
- Grade 3 endocrinopathy that is adequately controlled by hormone replacement;
- Grade 3 tumor flare.
- Any Grade 4 or 5 Adverse Event (AE);
- Any Grade 2 drug-related uveitis or eye pain or blurred vision that does not respond to topical therapy and does not improve to Grade 1 severity within 2 weeks OR requires systemic treatment;
- Any treatment-related Grade 2 or greater toxicity that persists and results in an inability to administer C2D1.

For events that are not included in the above definitions, the SMC may declare any additional specific toxicity to be a DLT.

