8.14.2. Observation and Recording of AEs

The subject will be required to report any AE that occurs after the main informed consent is signed. SAEs will be reported as outlined in Section 8.16 and recorded in the AE CRF. AEs or SAEs occurring after a subject signs the pre-screening ICF will not be collected.

Study personnel will assess AEs at every visit. The date of onset and resolution (if applicable) of the AE will be documented in the source documents and on the appropriate CRF page. The Investigator will monitor all AEs to the final visit or to a satisfactory resolution if the AE is ongoing.

All AEs will be recorded from the time of signed informed consent until the End of Treatment visit (28 days \pm 7 days after the last dose of JTX-2011, nivolumab, ipilimumab, or pembrolizumab, whichever occurred last), and are to be recorded on the appropriate AE pages in the eCRF and in source documents. AEs for the End of Treatment visit may be collected by a telephone contact if the patient is not able to attend an on-site End of Treatment visit. Where possible, a diagnosis rather than a list of symptoms should be recorded. If a diagnosis has not been made then each symptom should be listed individually.

All study drug related AEs/serious adverse events (SAEs) (see Section 8.16 for definition) will be followed to resolution (the subject's health has returned to his/her baseline status or all variables have returned to normal), or until new therapy initiated. Where appropriate, medical tests and examinations will be performed to document resolution of the event(s).

SAE Reporting Contact Information

Tel: [REDACTED]

Fax: [REDACTED]

Email: [REDACTED]

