## **8. ENDPOINT DEFINITIONS AND DERIVATIONS**

### **8.1 SAFETY DEFINITIONS AND ENDPOINTS**

#### **8.1.1 ADVERSE EVENT ENDPOINTS**

Adverse events will be categorized by pre-existing, treatment emergent and post treatment.

- Pre-existing AEs are designated to events that occur prior to the first dose of study drug(s) or observed prior to first dose but did not increase in NCI CTCAE toxicity grade during treatment period.
- Post-treatment adverse events will be any adverse events reported outside the 28 day post dose treatment window until the end of study participation. Any subsequent non-protocol treatment for the cancer diagnosis will end the potential study drug(s) adverse event data collection.
- Treatment-Emergent Adverse Events (TEAEs) are designated to events that occur after the start of study drug(s) and on or before 28 days after final dose of study drug, and were not observed prior to start of treatment; Or if the event was observed prior to the start of study drug but increased in NCI CTCAE grade after either the start of study drug or prior to 28 days after the final dose of study drug. Pre-existing adverse events may be reclassified as TEAEs if the frequency of the event increases during treatment.
- Treatment Related TEAEs will include those TEAEs which are possibly or probably related to study drug(s) as designated by the investigator. Events having a missing relatedness will be designated as definitely related on tables but the listing will display the data as collected. Relationship may be attributed by JTX-2011 and/or nivolumab/ipilimumab/pembrolizumab and will be displayed separately.
- Serious adverse events (SAEs) will include all events classified as serious on the eCRF. The electronic database used to enter data at the site (i.e., RAVE / iMedidata) will be deemed as the complete report for adverse event information. The pharmacovigilance database will be reconciled against the EDC.

- Infusion related reactions (IRRs) may be captured as an adverse event as well as the symptoms that cause the IRR. Symptoms of IRRs are events occurring shortly after or during the study drug infusion. Symptoms may include but are not limited to: flushing, headache, nausea, fever, chills, dyspnea, rash, hypotension, wheezing, coughing, tachycardia. Any sign/symptom determined to be associated with an IRR may be counted as such in adverse event reporting. The highest grade sign/symptom must be associated with the IRR preferred term.

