### 9.9.1 ADVERSE EVENTS

Adverse events (AEs) will be listed and summarized using MedDRA v19 coded terms. Listings will be created by categories for AEs as outlined below:

- All adverse events (AEs) with flags for treatment emergent adverse events (TEAEs) and flags of relatedness to study drug(s)
- SAEs with flags for treatment emergent adverse events (TEAEs) and flags of relatedness to study drug(s)
- Immune related adverse events (irAEs)
- Infusion related reactions (IRRs)
- TEAEs leading to death
- TEAEs leading to study drug interruption, reduction, hold or permanent study drug discontinuation
- TEAEs considered as DLTs

A general overview summary table will include frequencies by category of AE (as listed above) and will also include TEAE by severity grade and relationship to study drug (both JTX-2011 and/or nivolumab and/or ipilimumab and/or pembrolizumab).

Frequencies and percentages will be reported by System Organ Class (SOC) and Preferred Term (PT). Patients with multiple events for a category will be counted once in the highest CTCAE classification. Summary tables will include treatment-emergent AEs, unless specified otherwise. Missing onset date for an event will be considered as TEAE. If relatedness is missing the adverse event will be considered related. The denominator (N) for adverse events reported at each cycle will include SAF patients who are dosed at least once in that cycle. Important note: Patients will be counted in terms of number and adverse event in the actual dose group as received, not the as intended dose group. Summary tables by SOC and PT will be sorted in descending frequency of SOC for the total column, then in descending frequency of PT within SOC for the total column. Summary tables by PT will be sorted in descending frequency of PT for the total column.

The following summary TEAE tables listed in Table 7 below will be presented for Phase 1 and Phase 2 parts. In addition, DLTs will be summarized by SOC and PT only for Phase 1 parts (A, B, E, G) for DLT Evaluable Set.

Table 7 Summary of Adverse Event Displays

Category	TEAE	IRR	irAE	TEAE Related to JTX2011	TEAE Related to Any Study Drug	Serious TEAE	Related SAE	TEAE Resulting in Death	TEAE Resulting in Dose Interruption, Reduction or Hold	TEAE Resulting in Study Drug Discontinuation
SOC and PT	X			X	X	X	X			
SOC/PT/Max. Grade	X			X	X					
SOC/PT/Max. Grade $\geq 3$				X						
SOC/PT by Cycle	X									
SOC/PT by Grade, Cycle										

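### For q6w intervals with no day-22 partner dose, the single 28-day TEAE window closes about 14 days before the next planned dose, so a new event that stops treatment can drop out of the TEAE tables

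*SAP*

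**What the plan says.** SAP 8.1.1 defines TEAEs as "events that occur after the start of study drug(s) and on or before 28 days after final dose of study drug", with a provision for earlier events that worsen in grade. Events outside the 28 days are post-treatment. No rule in the SAP varies the window by schedule. SAP 9.9.1 restricts summary tables to TEAEs by default, and Protocol 9.4.8.1 agrees.

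The window runs from study drug, not from JTX-2011 alone. Protocol 3.6 states: "Study drug is hereby defined as JTX-2011 monotherapy and JTX-2011 in combination with nivolumab, ipilimumab, or pembrolizumab". Protocol 8.14.2 likewise times the End of Treatment visit from the point "after the last dose of JTX-2011, nivolumab, ipilimumab, or pembrolizumab, whichever occurred last".

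Cycles last 3 or 6 weeks (Protocol 7). In Part E, per Protocol 5.3, "JTX-2011 will be administered IV q6w and will be administered until a subject meets criteria for discontinuation", with ipilimumab every 3 weeks for up to four doses. Table 13 puts ipilimumab alone on day 22 of Cycles 1 and 2. Its footnote on missed doses allows make-up doses from C3D1. C64 is q6w monotherapy.

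DLTs are first-cycle toxicities. One criterion in Protocol 6.3 is "Any treatment-related Grade 2 or greater toxicity that persists and results in an inability to administer C2D1". SAP 9.9.1 plans a listing of "TEAEs considered as DLTs" and a separate DLT summary on the DLT Evaluable Set.

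On collection, Protocol 8.14.2 states: "All AEs will be recorded from the time of signed informed consent until the End of Treatment visit". That visit falls 28 ± 7 days after the last dose.

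**The concern.** A q6w subject five weeks after a JTX-2011 dose is still mid-cycle and awaiting the next one. If a new event then appears and dosing never resumes, the earlier dose becomes the final dose and the event falls outside the window. If dosing resumes, the same event is a TEAE. Classification therefore depends on whether the event ended treatment, and the rule removes the events that matter most for tolerability.

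Safety and tolerability are a primary objective, and Protocol 1.4.2.2 gives learning the q6w safety profile as a reason for testing that schedule. Protocol 6.2.2 already treats q6w as needing longer observation: the safety committee reviews at least 5 weeks of data (35 days) before escalating on q6w, against 2 weeks on q3w. SAP 9.1 uses the same 28 days for on-treatment deaths.

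**Working it through.** The 28 days is a definition, so there is no planned figure to reproduce. The check is day arithmetic.

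Inputs: window 28 days (SAP 8.1.1); planned intervals 21 or 42 days (Protocol 7); day-22 ipilimumab falls 21 days after that cycle's JTX-2011 dose (Table 13); ±3-day visit windows at C2D22 and C3D1 (Protocol 7.2.8 and 7.2.9).

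Let day 0 be the last JTX-2011 dose. Then:

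- window end = day of the last dose of any study drug + 28;
- uncovered days = next planned JTX-2011 day − window end, not below 0.

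| Interval | Last dose of any drug | Window end | Next JTX-2011 | Uncovered |
|---|---|---|---|---|
| q3w | 0 | 28 | 21 | 0 |
| q6w, no day-22 partner dose | 0 | 28 | 42 | 14 (14/42 = 33%) |
| Same, next visit 3 days late | 0 | 28 | 45 | 17 (17/45 = 38%) |
| Part E Cycle 1 or 2, day-22 ipilimumab given | 21 | 21 + 28 = 49 | 42 | 0 |
| Part E Cycle 2, day 22 at −3, next dose at +3 | 18 | 18 + 28 = 46 | 45 | 0 |

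The 14 days include the planned dosing day. Counting only full days before it gives 13 (13/42 = 31%).

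**Where the gap arises.** It arises in Part E once ipilimumab is finished, in Part E cycles without a day-22 dose, and in C64. The second case is partly built in: Table 5 and Protocol 6.7.3.3 have treatment restart after withholding with JTX-2011 alone, so subjects with earlier toxicity can have q6w intervals without ipilimumab.

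**DLTs in Part E.** With C1D1 as study day 1, 28 days later is study day 29 and C2D1 is study day 43. A DLT is outside the window only if onset is on study days 30 to 42, the C1D22 ipilimumab was not given and no later dose followed. Such an event meets Protocol 6.3 but not the heading of the DLT listing.

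**Collection.** The End of Treatment visit falls 28 − 7 = 21 to 28 + 7 = 35 days after the last dose. That is 42 − 35 = 7 to 42 − 21 = 21 days before the next q6w dose would have been due. A wider SAP window therefore recovers only events that were recorded.

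**The case against.** The strongest reply is that the gap is narrow and little is lost. Much of this stands.

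- A reader might infer that days 29 to 42 after every last q6w JTX-2011 dose are uncovered. They are not. The window runs from any study drug, so Part E Cycles 1 and 2 with day-22 ipilimumab are covered, as are later intervals in which a make-up ipilimumab dose falls on day 22.
- A reader might infer that DLTs vanish from the analysis. The documents do not support that. The DLT Evaluable Set (SAP 6.1.1) includes subjects with any DLT, and the separate DLT summary is not expressly limited to TEAEs, although the TEAE default for summary tables leaves this unclear. A toxicity that caused the day-22 dose to be withheld had already begun inside the window, and the persisting-toxicity criterion does not require late onset. Protocol 6.8.2 does not replace a subject who has had a DLT.
- A reader might infer that q6w rates are biased against q3w rates. SAP 7.10 plans no comparisons, and results are descriptive by part and cohort. What can be said is directional: treatment-ending q6w events can be undercounted.
- Collected events are not lost. SAP 9.9.1 lists all AEs with TEAE flags, and related SAEs are reportable at any time (Protocol 8.16.4). For a subject still awaiting the next dose, recording is open.
- The Protocol 1.6.3 warning on ipilimumab immune events, "However, they may occur weeks to months after discontinuation of ipilimumab", adds little, since a 42-day window would miss many of those too.

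What remains is that tables, not listings, carry the tolerability message, and no rule keeps a treatment-ending event in them.

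**Conclusion.** The point holds in this limited form. For planned q6w intervals with no day-22 partner dose, 14 of 42 days (33%) lie outside the TEAE window, against none of 21 under q3w. A new event there that ends treatment is misclassified as post-treatment. The DLT consequence is an edge case confined to the listing.

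The 33% is calendar time, not a share of events. The documents give no event rate by day, so the number reclassified cannot be computed.

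The exposed group is small. Part E was planned at about 18 subjects, and SAP 4 reports all Phase 1 parts completed. Parts F and H never opened. C64 was planned at about 15, but its enrolment cannot be confirmed: SAP 3.1.4 and 4 describe only C01 to C05, while SAP 5 still gives about 120 for Part C, which at 15 per cohort is the protocol's eight cohorts. Only subjects whose last dose was JTX-2011 without a later partner dose, and who had a new event in the gap, are affected.

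This should be fixed. It is not severe enough to block the analysis.

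**What to change.** In SAP 8.1.1, for q6w subjects:

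1. End the TEAE window at the later of 28 days after the last dose of any study drug and 42 days after the last JTX-2011 dose, or at new anticancer therapy if earlier. This leaves q3w unchanged, and also Part E cycles with day-22 ipilimumab (the later of 49 and 42 is still 49).
2. Count any event recorded as a DLT or as the reason for discontinuation as treatment-emergent regardless of the window. This also covers a next visit falling up to 3 days late. It removes the doubt over the DLT listing and summary.
3. State whether the on-treatment death count in SAP 9.1 follows the same window.

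Align AE recording in Protocol 8.14.2 and the footnotes of Tables 13 and 16 only for subjects still being followed. For those already finished, state in the report that events after the End of Treatment visit may be incompletely collected.

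The cost is SAP wording and programming, plus a later contact for any q6w subject still in follow-up. Reported q6w AE rates become slightly less favourable.

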1.6. Adverse Events

1.6.1. JTX-2011 Monotherapy

Based on the preclinical toxicology and observations thus far in this trial, JTX-2011 does not appear to cause spontaneous activation of the immune system nor does it induce pro-inflammatory cytokines at levels likely to induce cytokine storm, so the risk of acute

inflammatory reactions due to cytokine induction is predicted to be low. However, JTX-2011 may cause signs and symptoms of an infusion reaction or cytokine storm which may include the following: headache, fever, facial flushing, pruritus, myalgia, nausea, chest tightness, dyspnea, vomiting, erythema, abdominal discomfort, diaphoresis, shivers, hypertension, hypotension, lightheadedness, palpitations, and urticaria.

Subjects will be observed for at least 1 hour after completion of JTX-2011 infusion for assessment of IV infusion tolerability.

JTX-2011 may be expected to cause adverse events similar to other immunotherapy agents, with immune-related toxicities caused by immune stimulation in organs not involved by cancer. As such, immune-related adverse events which can involve any organ system may be seen. These include pneumonitis, colitis, hepatitis, endocrinopathies, nephritis, rash, and encephalitis (Opdivo® Full Prescribing Information {Bristol-Myers Squibb Company 2017a}).

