## 7.2 STANDARD SUMMARY STATISTICS

Summary will be provided separately for each Phase 1 part (A, B, E, G) by dose level and for each Phase 2 part (C, D) by tumor type cohort unless specified otherwise. A total column will also be provided in summary tables as appropriate. Descriptive statistics (n, mean, standard deviation, median, minimum and maximum) will be calculated for all continuous variables. Geometric mean, geometric coefficient of variation (GCV%), interquartile range (IQR:Q1-Q3) and 2 sided confidence intervals may also be presented as appropriate. For continuous parameters, the sample number will be displayed as a whole number. In general means and medians will be reported to one additional decimal place as compared to original data as collected and standard deviation will be reported to 2 additional decimal places. Minimums and maximums will be reported as collected. Data will be aligned by decimal place where appropriate. Column headers will have (N=) where applicable.

Frequencies and percentages will be presented for categorical and ordinal variables. Frequencies are not displayed for counts of zero. All frequency counts greater than 0 will have percentages displayed. Count and percentages will be displayed in the form xxx (xxx.x). All percentage columns will be right justified. Column headers will have (N=) and where applicable n (%).

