- Immune-related adverse reactions (irAEs) are unique side effects typically seen after dosing with checkpoint inhibitors. At a minimum, the following have been associated with irAEs and will be evaluated for incidence in the combination arms: pneumonitis, colitis, hepatitis, endocrinopathies (hypophysitis), adrenal insufficiency, hypothyroidism and hyperthyroidism, type I diabetes mellitus, nephritis (defined as renal dysfunction or  $\geq G2$  increased creatinine requiring corticosteroids), rash, encephalitis (neurologic signs/symptoms), others include: motor dysfunction, vasculitis, myasthenic syndrome. Some ipilimumab associated irAEs include but are not limited to: uveitis, iritis, pancreatitis, facial and abducens nerve paresis, demyelination, polymyalgia rheumatica, autoimmune neuropathy, Guillain-Barre syndrome, hypopituitarism, system inflammatory response syndrome, gastritis, duodenitis, and sarcoidosis.

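### SAP 8.1.1 ties the only irAE derivation to the combination arms, which contradicts the SAP's own irAE tables for all parts and the protocol's expectation of irAEs from JTX-2011 alone

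*SAP*

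**What the plan says.** SAP 8.1.1 introduces irAEs as a checkpoint-inhibitor effect: "Immune-related adverse reactions (irAEs) are unique side effects typically seen after dosing with checkpoint inhibitors". It then gives a minimum list of terms (pneumonitis, colitis, hepatitis, endocrinopathies, nephritis, rash, encephalitis and others) which, it says, "have been associated with irAEs and will be evaluated for incidence in the combination arms". No other section of the SAP says which events count as irAEs.

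SAP 9.9.1 names irAEs as a listing category and as a category in the general overview table. It continues: "The following summary TEAE tables listed in Table 7 below will be presented for Phase 1 and Phase 2 parts". Table 7 has an irAE column, marked for the summary by preferred term and for the summary by preferred term and cycle.

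The protocol's section on JTX-2011 monotherapy (1.6.1) says of the drug on its own: "As such, immune-related adverse events which can involve any organ system may be seen".

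**The concern.** JTX-2011 is an immune agonist, and the safety of monotherapy is a primary objective in both phases (SAP 3.1.1 for Part A, 3.1.4 for Part C). A derivation rule that names only the combination arms leaves monotherapy irAEs without a stated classification, although the tables that need it are planned.

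The harm would lie in interpretation. If the flag were derived literally, the Part A and Part C irAE tables could be blank, show zeros, or not be produced. A reader of the study report could take that as evidence that JTX-2011 alone causes few or no irAEs, and that those seen in the combination parts come from the partner drug.

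The DLT summary would not fill the gap. Protocol 6.3 exempts a Grade 3 irAE that resolves within 3 weeks on immunosuppressive therapy, so such an event would not be counted there under that criterion.

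**Working it through.** The plan gives no figure to reproduce. The check is a comparison of texts, with a count of the subjects in scope.

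**1. Scope in the derivation.** SAP 8.1.1 limits the incidence evaluation to the combination arms. Read literally, that covers Parts B, D, E and G and leaves out A and C. (SAP 4 says that Parts F and H never opened.)

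**2. Scope in the outputs.**
- SAP 9.9 uses the Safety Analysis Set for safety outputs, which includes all treated monotherapy subjects.
- SAP 7.2 sets the default layout: "Summary will be provided separately for each Phase 1 part (A, B, E, G) by dose level", with Phase 2 Parts C and D by tumor cohort, unless specified otherwise.
- SAP 9.9.1 and Table 7 put no restriction by part on the irAE column. The same section does restrict an output where that is intended: "DLTs will be summarized by SOC and PT only for Phase 1 parts (A, B, E, G) for DLT Evaluable Set".

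The outputs therefore include Parts A and C.

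**3. Which text governs.** The SAP does not say. Because the 7.2 default yields to anything specified otherwise, 8.1.1 can be read as the exception. Because 9.9.1 is the output plan and carries no exclusion, the opposite reading is equally available. Mock shells might settle the matter in practice, but SAP 7.1 keeps them outside the SAP signoff.

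**4. Is there another source for the flag?** For serious events, 8.1.1 relies on the eCRF classification. It names no such field for irAEs, so the term list is the only stated derivation.

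**5. Against the protocol.** Section 1.6.1 expects irAEs from monotherapy. Section 8.16.3 lists irAEs as expected with JTX-2011 as well as with the three partner drugs. Section 1.3 commits to close monitoring for irAEs in subjects treated with JTX-2011 alone and in combination. The synopsis (Safety Evaluation) says that irAEs will be assessed and sets no limit by part. None of these supports a combination-only scope.

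**6. Post-progression treatment in Part C.** Protocol 5.5 allows nivolumab, or later pembrolizumab, to be added after confirmed progression. SAP 8.1.1 does not say whether such a subject then belongs to a combination arm.

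**7. Subjects in scope.**
- Part A: 27 + 12 = 39 enrolled (Protocol 5.1).
- Part C: 5 × 15 = 75 planned on the five cohorts in SAP 4, or 8 × 15 = 120 on the eight cohorts in Protocol 5.5. SAP 5 also gives 120.
- Together: 39 + 75 = 114 to 39 + 120 = 159.

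This counts the subjects whose irAE classification is unclear. It does not count subjects with an irAE.

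**8. Term list.** Protocol 8.16.3 names dermatitis, enterocolitis, pruritus and vitiligo, none of which is on the 8.1.1 list. The 8.1.1 list is open-ended, so they may be added, but they are not pre-specified.

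**The case against.** The strongest reply is that the analysis section already covers monotherapy. SAP 9.9.1 plans the irAE listing, the overview row and the Table 7 summaries for the parts of both phases, and nothing in 8.1.1 says that monotherapy is excluded. The word *only* does not appear, Parts A and C are not mentioned, and the list is introduced as a minimum. This stands. A reader might infer that JTX-2011 monotherapy will get no irAE incidence at all, and the documents do not support that inference.

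Nor would an event be lost. A case of colitis or hepatitis in Part A or C would still appear in the treatment-emergent tables by SOC and preferred term and by maximum grade, in the tables of events related to JTX-2011 if so attributed, and in the adverse event listings. At worst, the grouped irAE presentation is affected.

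The SAP also summarises each part separately and makes no comparisons (7.2, 7.10), so a monotherapy column printed beside combination columns is not a planned layout. That weakens the argument about attribution but does not remove it, because readers of a multi-part report will compare the tables themselves.

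The reply does not dispose of the conflict. The sole derivation names one scope and the outputs another, and nothing signed says which prevails.

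**Conclusion.** SAP 8.1.1 is wrong as written. Its scope for irAE incidence contradicts SAP 9.9.1 and Table 7, and is at odds with Protocol 1.3, 1.6.1 and 8.16.3. The consequence is conditional: if 8.1.1 is programmed literally, the grouped irAE summaries would omit or understate monotherapy irAEs. Whether that would happen cannot be told from the documents.

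The parts concerned hold 114 to 159 subjects, taking Part A as enrolled and Part C as planned. It is tempting to multiply that by a plausible irAE rate and report a number of subjects left out. Neither document gives a rate, and the product would also assume total omission, so no such count is offered.

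The point merits correction before database lock because it touches a primary safety objective and is simple to put right. It should be described as an inconsistency to reconcile, not as a missing analysis.

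**What to change.** In SAP 8.1.1, replace the restriction to the combination arms with *in all parts, including JTX-2011 monotherapy (Parts A and C)*. One pre-specified term list then feeds the irAE listing, the overview row and both Table 7 irAE summaries. It also settles whether the flag applies to Part C subjects who add a PD-1 inhibitor after progression.

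Optionally, align the list with Protocol 8.16.3 by adding dermatitis, enterocolitis, pruritus and vitiligo, or state that the existing terms are meant to cover them.

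The cost is one phrase, at most four added terms, and the re-approval that SAP 2 requires for any update. No new data are needed.
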